1. Self-report of significant incontinence in the 6 months prior to prostatectomy. Based on data from the Prostate Cancer Outcomes Study,² we would expect about 14% of potential participants to have any pre-existing incontinence, 10% with minor leakage. In our pilot study of a clinic-based intervention at the Birmingham VAMC (Preliminary studies Section - Study #5), 2 of 30 men scheduled for prostatectomy (7%) had minor incontinence prior to prostatectomy and none of them had severe incontinence. In our prior clinical trial of preoperative pelvic floor muscle training for men undergoing radical prostatectomy, we operationalized this exclusion as “no more than 2 incontinence episodes in the last 6 months, not including post-void dribbling” and will do the same for the current proposal.⁴ Men who are excluded will be offered referral to the VA Continence Clinic for perioperative rehabilitation.

Sample size

Given the primary outcome is time to event, survival analyses will be used to conduct the analyses. A one-sided log rank test with an overall sample size of 156 subjects (of which 78 are randomized to standard care and 78 are randomized to Telehealth) achieves 80% power using a one-tailed 0.05 significance level to detect a difference of 0.2000 between 0.55 and 0.35 - the proportions remaining incontinent in the two groups surviving in standard care and Telehealth respectively. This effect corresponds to a hazard ratio of 1.756. These results are based on the assumption that the hazard rates are proportional. The proposed effect size is based on our earlier research.⁴ Power and sample size has been calculated using the Log-Rank procedures within PASS 11.0 (Hintze, J. (2011). PASS 11. NCSS, LLC. Kaysville, Utah, USA. www.ncss.com).

In our pilot study, after randomization, 10% of Veterans decided to have radiation instead of radical prostatectomy or were found to have positive lymph nodes during surgery and their prostatectomy aborted. These men ended participation in the study because they no longer had the risk factor for incontinence. To recruit sufficient numbers of Veterans so that we obtain the full 156 subjects indicated by our power calculation above, we will plan to randomize 10% more Veterans for a total of 172. When we reach the total of 156 Veterans having had a radical prostatectomy, we will end recruitment.

Recruitment Procedures at the VAMC

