2. Gleason Score (<7 and 7 or greater) - named after Donald Gleason, a pathologist at the Minneapolis VAMC who developed this important tool with other colleagues in the 1960s, to classify the differentiation of the cancer cells in the prostate biopsy; the higher the score, the more anaplastic the tumor pattern, and the more likely that the tumor has spread beyond the prostate. The Gleason score serves as an indication of the likely extent of prostate cancer and serves as a surrogate for the surgical margins that will be necessary to resect the cancer, which will occur after randomization. The more extensive the resections are associated with worse continence outcomes, contingent particularly on whether one or both neurovascular bundles could be preserved. *Seven is considered the cut point for higher risk disease.*

Within each stratum, blocked randomization will be performed using a variable block size and a table of random numbers to avoid inequity in the total number of subjects assigned to each group. Stratification will be used *only* to ensure that the treatment groups are similar on severity and treatment factors, not to compare groups. Each site will have a separate randomization schedule to avoid unequal distributions between sites. Also, blocking is used not to create comparison groups but only to ensure that the groups are similar in size.

Intervention

This telehealth technology allows for daily guidance via a series of interactive screens. At the time of his choosing each day, the participant interacts with a 10-minute session. Informational screens are interspersed with screens that pose questions. Some questions are on understanding of a technique, some on adherence to the rehabilitation program. Depending on the participant's answers, the telehealth program's branching logic permits different paths. For example, if the participant answers that he has not yet resumed his exercises postoperatively, the next screen will inquire about the reason. Four common reasons are listed, and appropriate information and instructions are provided depending on his endorsement of a reason. Some responses, such as repeated failure to resume exercises postoperatively, a lapse in adherence to exercises preoperatively once adherence is established, failure to master a specific skill such as urgency suppression, or

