up or down depending on the error rate detected. Manual inspection of the forms will be done to resolve differences in the dually entered data. The principal investigator and statistician will meet with the database manager to review accrual, data entry, and examine the database for outliers or data base entry errors monthly.

Data Analysis

Preliminary Analyses

Although subjects will be stratified and randomized, the equivalency of the two groups will be evaluated on selected variables that might influence treatment outcome: study site, age, nerve sparing surgery, body mass index. The chi square statistic will be used for the categorical variables and the two-sample t test for continuous variables. Normality will be carefully assessed for continuous outcomes and if the assumption is violated, non-parametric methods will be used.

Outcome Variables Analysis

Primary outcome analysis: duration of incontinence (time to achieve continence after surgery). Participants will be considered continent if they answer that they leak urine “never” on the ICIQ-SF for 3 weeks in a row. Please see Methodology section for complete explanation of this measure. Baseline time for this measure will be the day of surgery. Median time until continence and its 95% confidence interval will be calculated per group. The duration of incontinence will be examined using the Kaplan-Meier procedure, in which all protocol eligible participants are analyzed. Men who did not have a prostatectomy – either due to positive lymph nodes during surgery or because they changed their mind and selected another treatment after randomization but before surgery will not be included in the analysis. All other men randomized will be included. The duration of incontinence will be compared between the 2 groups using the log rank test. We will also compare continence rates at 9 and 12 months.

Secondary outcome analyses (severity of incontinence, impact on quality of life, and patient reported evaluations of improvement and satisfaction with treatment) will be measured by:

1. ICIQ-SF total score
2. EPIC-UI total score
3. Pad use from the EPIC-UI
4. Patient estimation of improvement measured by the GPI and EPI
5. Patient satisfaction as measured by the PSQ
6. IIQ – total and subscale scores
7. IPSS Quality of Life Question (IPSS QoL)
8. Questions on activity restriction, amount of disturbance caused by incontinence
9. Return to work or normal activities after surgery.

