Our hypothesis for the secondary outcomes is that total ICIQ-SF, EPIC-UI total Score, Pad use, GPI, EPI, PSQ, IIQ, IPSS QoL, return to work or normal activity, and amount of disturbance caused by incontinence will be better in the pelvic floor muscle rehabilitation group.

Initially, descriptive analyses will be conducted to examine distributions of the frequency of symptoms and possible covariates. Extreme values will be checked for accuracy and recoded as indicated. Transformations may be employed to correct for skewness or heterogeneity as needed.

The ICIQ-SF total score and the EPIC-UI total score will be analyzed using multiple regression analysis to regress the 6 and 12-month scores on treatment group, while controlling for baseline score (first score after catheter removal post-operatively). Pad use will be dichotomized into no pad use and any pad use. Pad use will also be analyzed descriptively as no pads, 1 pad, or 2 or more pads. The chi square statistic and the t test for independent samples will be used. Both measures are necessary for comparison with earlier studies. Multiple regression will be used for the GPI, EPI, and PSQ at 6 and 12 months. There is no baseline for these measures as they are the patients’ evaluations of their improvement and treatment satisfaction. For the IPSS QoL question, questions on activity restriction, disturbance, and return to work or normal activity, the chi square statistic and the t test for independent samples will be used.

Qualitative Analysis

To ensure analytic rigor, the following procedures will be followed: (1) data immersion (reading/listening and re-reading/listening to the text); (2) thematic identification and articulation (discovering, naming, defining codes/variables); (3) data categorization (developing a coding scheme); (4) pattern articulation (identifying connections within and between codes); (5) data interpretation (recognizing how the patterns transcend individual experiences and reflect larger social processes). As an analytical process, content analysis involves sorting and making sense of written and narrative data. The goal is not to generalize across a population, but rather to provide understanding and explanation from the respondent's perspective.

DISSEMINATION PLAN

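### The GPI, EPI and PSQ regressions name no covariates, and the factors the trial randomises by (age group, Gleason group, site) enter no outcome model

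*Combined protocol and SAP*

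**What the plan says.** Stratification and Randomization: allocation is stratified by age (split at 65) and Gleason score (split at 7), and each site has its own schedule. Gleason score is used as a stand-in for the margins needed to "resect the cancer, which will occur after randomization". The same paragraph links preservation of the neurovascular bundles to continence.

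Data Analysis, Preliminary Analyses: "the equivalency of the two groups will be evaluated on selected variables that might influence treatment outcome". The variables are study site, age, nerve sparing and body mass index. "The chi square statistic will be used for the categorical variables and the two-sample t test for continuous variables". No significance level is given, and nothing is said about what follows from a significant result.

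Data Analysis, Outcome Variables Analysis: the primary comparison is a log rank test with no strata or covariates mentioned. For the secondary outcomes, descriptive analyses will "examine distributions of the frequency of symptoms and possible covariates"; the covariates are not named. The ICIQ-SF and EPIC-UI regressions are specified as treatment group plus a baseline score, defined as the first score after the catheter comes out. For the three patient ratings the plan says only: "Multiple regression will be used for the GPI, EPI, and PSQ at 6 and 12 months". It adds that these measures have no baseline.

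**The concern.** Three outcomes at two times make six regressions whose right-hand side is not written down beyond, presumably, treatment group. The trial builds its allocation on three factors it regards as prognostic and then leaves them out of every model. When a prognostic factor is balanced by design but ignored in the analysis, the treatment estimate varies less than its standard error says. The test becomes conservative and power is lost.

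The plan's only list of influential variables is a poor source for filling the gap. It lacks one of the two stratifiers, and it contains a variable that arises after randomisation. It is also tied to significance tests, and a non-significant test is not evidence that the arms are alike. Because the covariates are open, they could also be chosen after the data are seen.

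**Working it through.** **1. The plan's own figure.** Sample size states: "A one-sided log rank test with an overall sample size of 156 subjects" "achieves 80% power using a one-tailed 0.05 significance level to detect a difference of 0.2000 between 0.55 and 0.35", and "This effect corresponds to a hazard ratio of 1.756".
- Hazard ratio: ln 0.35 / ln 0.55 = 1.756, as stated.
- Expected events: 156 × [1 − (0.55 + 0.35)/2] = 156 × 0.55 = 85.8.
- Freedman power, one-sided 5%: Φ(√85.8 × 0.756/2.756 − 1.645) = Φ(0.896) = 81.5%, close to the stated 80%.

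No covariate enters this calculation, so nothing below changes it.

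**2. The variables side by side.**

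| Variable | Governs allocation | In the equivalency check | In an outcome model | Settled before randomisation |
|---|---|---|---|---|
| Age | yes (split at 65) | yes | no | yes |
| Gleason score | yes (split at 7) | no | no | yes |
| Site | yes (own schedule) | yes | no | yes |
| Body mass index | no | yes | no | timing not stated |
| Nerve sparing | no | yes | no | no |

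**3. What the balance tests can tell.** The 5% two-sided level is assumed, as none is given.
- At least one significant result by chance in four independent tests: 1 − 0.95⁴ = 18.5%. Counting only the two variables that do not govern allocation: 1 − 0.95² = 9.75%.
- With 78 per arm, the power to detect a nerve-sparing difference (assumed rates, normal approximation) is 26% for 60% v 70% and 52% for 60% v 75%. A passed test is weak evidence of similarity.

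**4. What the randomisation factors are worth.** From the plan: 78 per arm. Assumed: a continuous outcome, an effect of 0.4 SD, a two-sided 5% test, and R² (the share of outcome variance explained by age group, Gleason group and site) of 0.05, 0.10 or 0.20.
- Unadjusted standard error: √(2/78) = 0.160 SD. Ratio of effect to standard error: 0.4/0.160 = 2.498. Power: Φ(2.498 − 1.960) = 70.5%.
- Adjustment multiplies the standard error by √(1 − R²). The ratio becomes 2.563, 2.633 and 2.793, and power 72.7%, 75.0% and 79.8%.
- If balance were perfect and the factors were ignored, the type I error would be 2Φ(−1.960/√(1 − R²)) = 4.4%, 3.9% and 2.8%.

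Simulation with stratified blocks and 156 men:

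| Assumed R² | Type I error, factors left out | Power, left out | Power, included | Gain (points) |
|---|---|---|---|---|
| 0.05 | 4.8% | 72% | 73% | 1 |
| 0.10 | 4.3% | 70% | 74% | 4 |
| 0.20 | 3.0% | 71% | 79% | 8 |

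A repeat with 10,000 trials per setting (three equally likely sites, blocks of 4 or 6) gave gains of 1.6, 3.6 and 7.4 points.

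**5. What open covariates permit.** Null simulation: 156 men, four independent covariates, assumed total R² of 0.1, 0.2 and 0.3, two-sided 5%, 3,000 trials per setting.

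| Rule | Type I error | Standard error of the estimate |
|---|---|---|
| No adjustment | 5.1%, 5.3%, 4.8% | 0.161, 0.162, 0.157 |
| Adjust only for covariates with p < 0.05 between arms | 4.8%, 5.0%, 4.0% | 0.159, 0.158, 0.151 |
| Adjust for all four | 5.0%, 6.0%, 4.6% | 0.155, 0.149, 0.135 |
| Most favourable of all subsets | 9.0%, 11.1%, 11.7% | not computed |

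Selection by balance test does not inflate error but forgoes most of the precision. Only a free choice among covariate sets inflates it.

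**The case against.** The strongest reply is that nothing in the plan depends on the balance tests. A reader might infer that covariates will be picked by those tests. The documents do not say so: the tests are never called a screen, and the one mention of possible covariates concerns descriptive distributions. That objection stands, and the point here does not rest on the link.

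The remark that the ratings have no baseline may simply mean that the baseline term is dropped, leaving treatment group alone. That reading is possible. It still leaves out the randomisation factors, and the text does not settle it.

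A reader might also infer that all the planned regressions are unspecified. That is wrong, since ICIQ-SF and EPIC-UI have a named covariate.

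On nerve sparing, the plan does not call it a baseline variable and puts it in no model. It is also fair to look at comparability in the analysed set: men without prostatectomy are excluded (10% in the pilot), and stratifying at 65 does not fix continuous age. What fails is only the use of p-values as evidence of equivalence.

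Finally, the power figures suit EPI best. Figure 4 shows GPI with five categories and PSQ with three, although the text describes PSQ as a visual analogue scale. This limit stands. The plan's statement that stratification is not meant to compare groups rules out comparing strata; it does not bar the factors as covariates.

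**Conclusion.** The point holds in a limited form. Six secondary regressions lack named covariates, the randomisation factors appear in no outcome model, and the only list of influential variables is unsuited to supply them. For a continuous outcome and an assumed 0.4 SD effect, including the factors gains about 1 to 8 points of power as R² goes from 0.05 to 0.20. The effect size, R² and two-sided level are assumptions; the documents give none of them for these outcomes. The gain for GPI and PSQ, if analysed as categories, is not quantified here.

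The 9.0% to 11.7% error rates show what a free choice of covariates could do. They do not predict what this trial will do, and nothing in the documents suggests such a choice is intended. Nor would it be right to conclude that the primary result is at risk: the log rank test, the 156 men and the stated power do not change.

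**What to change.** In Outcome Variables Analysis, state that the GPI, EPI and PSQ regressions at 6 and 12 months include treatment group, age group, Gleason group and site, whatever the observed balance and with no selection by test. Body mass index may be added if it is named in advance. Nerve sparing is not to be used for adjustment. Define site as the unit that has its own randomisation schedule, since affiliated clinics recruit alongside the VA centres. State the model type for each rating to match its response format.

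In Preliminary Analyses, replace the tests and the word equivalency with a descriptive table by arm that includes Gleason group. Report nerve sparing separately as a surgical variable arising after randomisation.

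The cost is wording and a few degrees of freedom: 1 + 1 + 2 = 4 with three sites, or 1 + 1 + 5 = 7 if the three VA centres and three affiliated clinics count separately. The three factors must already be known for allocation, so no new data are needed.

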The control group is designed to control for the daily use of a telehealth program (an attention control) as well to equate basic information about urinary incontinence between groups. The control program matches the number of interactions but is limited to general prostate cancer information; perioperative care; wetness, odor and skin care management but no content on pelvic floor muscle training and bladder control strategies. Outcome measures will be administered by the telehealth program in both groups. For the Health Buddy, data are stored on the telehealth program and transmitted each night via toll-free telephone lines to a database behind a secure VA firewall as they are in the CCHT program. This was proven to be feasible and practical in our pilot study. For the web-based program, the data will be stored on a secure website with VA-approved encryption. Both groups will have use of the telehealth program monitored and quantitated. Preoperatively and 2 months postoperatively, telehealth sessions will be daily. After 2 months postoperatively, both groups will log-in weekly for outcomes measurement until 6 months postoperatively and two more times at 9 & 12 months postoperatively. If we cannot obtain a response through the telehealth program, the questionnaires will be mailed to the participants along with a postage-paid return envelope. These measures are delineated in detail in the Outcome Measures section and in Table 5. The telehealth content for each session for both groups ends with a "fun fact" including sports and other trivia, famous men who have done well after prostate cancer diagnosis, etc. which have been successfully implemented in the pilot study and promoted adherence to the daily home telehealth program, in our pilot study as well as in the CCHT programs VA wide. At 12 months, Veterans still incontinent in both groups will be offered treatment in the GRECC Continence Clinics or the VA Urology Clinic.

THEORETICAL FOUNDATION

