Birmingham site - Patients who are planning to undergo a prostatectomy at UAB will be informed of the study by their urologist at their pre-operative appointment at The Kirklin Clinic. The urologist will put a sentence in his clinic note that the patient has been informed about the study and agreed to have a study coordinator call him with more information. The urology nursing staff will email the study coordinator (secure UAB email to secure UAB email) with the names, MR numbers, and phone numbers of all patients who agree to be called. We will not be conducting any study procedures in The Kirklin Clinic. Our study coordinator will call the patient and explain the study to him. If he agrees to participate, she will conduct an informed consent discussion, answer all the patient's questions and mail the VA consent form, the VA HIPAA and the UAB HIPAA form - Authorization for Use/Disclosure of Health Information for Research form. Should the patient wish to meet in person rather than do a telephone consent, we will meet with them at the TKC Urology Clinic during an already scheduled appointment or at the BVAMC (whatever the patient prefers). If the patient has questions once he receives the consent form in the mail, he can call and have a second discussion with the study coordinator and/or arrange an in-person visit. Should the patient request an in-person visit and provide us with a signed consent form at that visit, we will transport the consent form in a locked bag from The Kirklin Clinic to the Birmingham VAMC.

Philadelphia and Atlanta sites – Recruitment at the Affiliate Urology Clinics at Philadelphia and Atlanta will be developed by the site and approved by their VA and University IRBs as appropriate with local regulations.

Stratification and Randomization

In order to assure between-group comparability, subjects will be stratified on two dimensions with possibility of impacting outcome:

1. Age (<65 years and 65 or older) – older men are more likely to have post-operative incontinence.

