The primary patient outcome is time to continence as measured by the ICIQ-SF. The ICIQ-SF is designed, in part, to screen for incontinence and is completely appropriate to determine if a person no longer has incontinence. We used time to continence in our previous clinical trial of preoperative training to prevent post-prostatectomy incontinence.⁴ Time to continence also has face validity since it is extremely important to the patient who wants to regain continence as soon as possible after his surgery. The ICIQ-SF will be completed weekly for 6 months post-operatively via the telehealth program. Each telehealth screen related to the ICIQ-SF will be prefaced with "During the last week" to make the timeframe clear. When a participant reports no incontinence on the ICIQ-SF (an answer of "never" to "In the last week, how often did you leak urine?") for 3 weeks in a row, we will consider him continent. We successfully used the definition of no reported leakage for 3 weeks based on weekly bladder diaries in our prior study of preoperative training to prevent post-prostatectomy incontinence.⁴ Although it is likely that participants who achieve this endpoint may still have occasional leakage, such as with heavy lifting or a good laugh, experience has shown that these men do not consider themselves incontinent. The total score of the ICIQ-SF will also be used to evaluate patient outcomes. The ICIQ-SF score has shown sensitivity to change with treatment in men with post-prostatectomy incontinence.²⁶ We will also compare continence rates at 9 and 12 months.

Secondary Outcome Measures

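### No between-group effect estimate is planned for time to continence; a hazard ratio stratified by age and Gleason group, with a matching log-rank test, is a cheap improvement

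*Combined protocol and SAP*

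**What the plan says.** In the combined protocol and SAP, the primary outcome paragraph under Data Analysis measures time from the day of surgery and uses the Kaplan-Meier method. It then gives one summary per arm, "Median time until continence and its 95% confidence interval will be calculated per group", and one comparison, "The duration of incontinence will be compared between the 2 groups using the log rank test". It names no strata, covariates, hazard ratio, difference in medians or between-group confidence interval. It adds "We will also compare continence rates at 9 and 12 months", without a method.

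The Sample size section puts the effect on a hazard ratio scale: "This effect corresponds to a hazard ratio of 1.756". It adds: "These results are based on the assumption that the hazard rates are proportional". It gives no time point for the proportions 0.55 and 0.35.

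Under Stratification and Randomization, "subjects will be stratified on two dimensions with possibility of impacting outcome": age (under 65, or 65 and over) and Gleason score (under 7, or 7 and over). Each site has its own schedule. The section also says that stratification serves only to make the groups alike and not for group comparison.

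On data collection, Outcome Measures states: "The ICIQ-SF will be completed weekly for 6 months post-operatively via the telehealth program". The Overview adds log-ins "two more times at 9 & 12 months postoperatively".

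**The concern.** A log-rank test tells the reader whether the arms differ, not by how much. The trial is meant to support VA-wide dissemination, so the size of the benefit matters. The hazard ratio on which the trial is sized is never estimated, and proportional hazards is never checked.

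The other planned items are weak substitutes. Two per-arm medians with separate intervals give no interval for the contrast, and the control median may not be reached while weekly data are collected. The 9- and 12-month comparison uses single assessments, to which the definition of continence (three consecutive weekly reports of no leakage) cannot be applied. It is therefore a different quantity.

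The second part is smaller. Age and Gleason score were chosen because they may affect outcome. If they do, a test that ignores them gives up some power.

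**Working it through.** **Inputs from the documents.** N = 156 (78 per arm), one-sided 5%, 80% power, 0.55 and 0.35 still incontinent (Sample size); weekly data to 6 months (Outcome Measures).

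**Assumptions.** Exponential times, censoring at week 26, no dropout. The documents state none of these.

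**The plan's own figure.** ln 0.35 / ln 0.55 = 1.756, as stated. Expected events are 156 × (1 − 0.45) = 85.8. Power at 85.8 events is 81.5% by Freedman's formula and 83.2% by Schoenfeld's. The stated 80% is met.

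**Would the per-arm medians be available?** If 0.55 applies at m months, the chance that a control man is continent by 6 months is 1 − 0.55^(6/m). The median is not reached when at most 38 of 78 men have the event. The upper log-log 95% limit needs at least 48 events.

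| 0.55 applies at | Control median not reached | Upper 95% limit reached |
|---|---|---|
| 6 months | 78% | 0.2% |
| 5 months | 37% | 4% |
| 4 months | 4% | 38% |
| 3 months | under 0.01% | 95% |

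The telehealth median is not reached in 0.2% of trials at 6 months, and less often at earlier time points.

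The rows below 6 months depend on the hazard shape. With an event-free first month, the 5-month figure falls from 37% to 28% and the 4-month figure from 4% to 0.7%; the 4-month upper limit is then reached in 66%. With a declining hazard (Weibull shape 0.6), the 4-month figure rises from 4% to 24%.

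**What would a hazard ratio show?** SE(log HR) = 2/√85.8 = 0.216. If 1.756 were observed with 0.55 applying at 6 months, the 90% CI would be 1.23 to 2.50 and the 95% CI 1.15 to 2.68. With 0.55 applying at 3 months there would be about 123 events and a 95% CI of 1.23 to 2.50. The week-26 difference would be 20 points with SE √(0.55 × 0.45/78 + 0.35 × 0.65/78) = 0.078, so a 95% CI of about 5 to 35 points.

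**What does stratifying change?** Simulation of 20,000 trials per setting, blocks of 4 and 6 in 12 cells. Further assumptions: 40% aged 65 or over, 65% Gleason 7 or over, three sites split 40/30/30. Arms were calibrated to 55% and 35% incontinent at 6 months. The factor hazard ratios are assumptions, since the documents give none.

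| Factor HR (each) | Unstratified | 4 strata | 12 cells with site |
|---|---|---|---|
| 1 (not prognostic) | 83.2% | 82.7% | 81.8% |
| 0.7 | 83.6% | 83.9% | 83.0% |
| 0.6 | 83.9% | 85.5% | 84.4% |
| 0.5 | 84.8% | 87.8% | 86.8% |

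A separate run gave changes from stratifying of −0.3 points (83.6 to 83.3%), +0.6 (84.0 to 84.6%) and +3.8 (84.9 to 88.7%) at factor HR 1, 0.7 and 0.5. If 0.55 and 0.35 apply at 3, 4 or 5 months, unstratified power is about 93, 90 and 87%, with similar changes from stratifying.

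One-sided type I error at factor HR 1, 0.7 and 0.5 is 5.0, 4.6 and 4.3% unstratified, and 4.9, 4.8 and 5.0% with 4 strata.

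**The case against.** The strongest reply is that the unstratified test is a stated choice. The Stratification and Randomization section limits the strata to making the groups alike and sets them apart from group comparison. It can also be read as excluding subgroup comparisons, but the first reading is fair. On that reading nothing in the plan is wrong, and this is why stratifying is offered here as an improvement and not as a correction. The section gives no statistical reason against a stratified test.

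Second, four strata omit site, which is also part of the randomisation. That is true. Twelve cells average 156/12 = 13 men and cost about 1 point of power against four strata in every setting, though they still beat no stratification at factor HR 0.5. Four strata, with site adjustment as a sensitivity analysis, is one defensible choice among several.

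Third, the median figures swing widely with an unstated time point and an assumed hazard shape. This stands: they show that the medians may fail, not that they will.

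Fourth, the plan checks group equivalence on site, age, nerve sparing and body mass index. That check estimates no treatment effect, and Gleason score is not in the list.

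Finally, nothing prevents the investigators from reporting a hazard ratio anyway. But an estimate chosen after the data are seen invites selection among measures.

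**Conclusion.** The gap is real but moderate, and worth closing. No between-group estimate with a confidence interval is planned for the primary outcome, and the planned control median may be unavailable in anything from almost no trials to 78% of them, depending on when 0.55 applies. The stratification part is minor: from about half a point of power lost to 3 or 4 points gained, over assumed factor hazard ratios of 1 to 0.5.

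Two stronger readings are tempting and are not supported. A reader might infer that leaving out the strata makes the primary test invalid or the trial underpowered. It does neither: in these simulations type I error stays at or below 5%, tending to the conservative side when the factors are prognostic, and power stays above 80% if the assumed proportions apply by 6 months. A reader might also infer that the control median cannot be estimated. That would need 0.55 to apply at about 6 months, which the documents do not say.

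**What to change.** 1. Pre-specify a hazard ratio for time to continence from a Cox model stratified by age group × Gleason group (4 strata). Give the 95% CI and the two-sided 90% CI, which matches the one-sided 5% test.
2. Stratify the primary log-rank test by the same 4 strata, so that test and estimate agree. Keep the unstratified log-rank test, on which the power calculation rests, and a site-adjusted Cox model as sensitivity analyses.
3. Report the week-26 Kaplan-Meier difference with its CI in all cases. Reporting it only if proportional hazards fails would let the data choose the estimate.

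Item 1 matters most.

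Cost: no new data or participants are needed, since the factors are known at randomisation. Stratifying loses about half a point of power if age and Gleason score are not prognostic. The stratified hazard ratio is conditional and differs slightly from 1.756 (about 1.78 at factor HR 0.7 and 1.85 at 0.5), so the plan should name the headline estimate. The Overview refers to participants already in the program at the 2015 vendor change, and Table 2 starts data analysis in Year 1. The change should therefore be a dated amendment, made without sight of results by arm.
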